2020

IMPROVE AKI Cluster- Randomized Trial (IMPROVE-AKI)

NCT03556293

09-21-2020

Statistical Analysis

We estimated the effect of both the implementation strategy and information support interventions, as well as their interaction, using hierarchical logistic regression models for 7-day postprocedural AKI. Models were fit using patient-level data with and without adjustment for the 20 patient-level characteristics in the VA-derived AKI risk prediction model underlying the Surveillance dashboard.²³ To account for site-level variation, observations were clustered at the site level, and models included a site-level random effect and controlled for site baseline risk-adjusted performance (observed to expected outcome ratio) in the 12 months before the study period. The decision to adjust for site baseline risk adjusted performance and other patient characteristics was prespecified. We implemented Satterthwaite small-sample correction because of the small number of clusters. Interim analyses and stopping criteria were not performed when determining sample size. In all models, the key features of interest were the interaction between implementation strategy and information support interventions, as well as differences across the four intervention combinations, with Assistance specified as the reference intervention. We estimated odds ratios (ORs) and 95% confidence intervals for pairwise comparisons of each combination of interventions and applied the Bonferroni correction for multiple comparisons. Analyses were run for the entire population and separately within the CKD subset. Corresponding sensitivity analyses modeled 30-day postprocedural AKI. Analyses were conducted using R 4.1.2.²⁶

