The proposed trial is guided by the Promoting Action on Research Implementation in Health Services (PARIHS) framework.⁴⁹⁻⁵⁵ The PARIHS framework and its three dimensions (context, facilitation, and evidence) was selected for addressing these barriers to implementation in AKI prevention.⁵⁴

C.2.a. Study Population: Site Inclusion and Exclusion Criteria. All patients at the participating sites will be enrolled into the trial with a series of inclusion and exclusion criteria.

VA Site Inclusion Criteria: All VA medical centers with a cardiac catheterization laboratory are eligible, and all catheterization operators at a site are included.. We currently have over-recruited 29 VA sites, but a minimum of 16 VA sites will be enrolled.

Patient Inclusion Criteria: Among these sites, only patients aged 18 or greater who undergo diagnostic coronary angiography or percutaneous coronary intervention (PCI or angioplasty) will be enrolled in the trial. CKD is of primary interest and it will be determined by a pre-existing CKD diagnosis in the VA medical record, or by two or more estimated glomerular filtration rates <60 (ml/min/1.73 m²) at least 90-days apart prior to presentation. **Patient Exclusion Criteria:** Patients with a history of dialysis (hemodialysis, peritoneal dialysis) or under the age of 18 will be excluded. Cardiac catheterization (also referred to as coronary angiography) is defined as a procedure in which a catheter is inserted into the femoral or radial artery and is threaded to the cardiac vasculature where radio-contrast dye is administered and a series of x-rays obtained in order to visualize the coronary arterial anatomy. PCI is when a clinical intervention is then performed to address any treatable pathology that is found.

C.2.b. Randomization. Randomization will occur at the hospital level in a 2x2 factorial design.⁴⁸ We will enroll a minimum of 16 Veteran Affairs (VA) hospitals with cardiac catheterization laboratories from across the United States (see Letters of Support and Facilities) that meet the medical center inclusion/exclusion criteria above. We will use a random number generator and block-randomize centers by the following variables: 1)

PROTOCOL

(Version #: 6, version date: 9-21-20)

VA region (1-4); and 2) patient volume (<800, 800+), see **Table 1** for the sites that initially met out inclusion/exclusion criteria.

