C.11. Sample Size and Power. To be conservative, power calculations assume the two-factor ANOVA with interaction. The target enrollment of approximately 2,644 is planned in each of the four arms of the study (TA, TA+ASR, VLC, VLC+ASR) with four hospitals within each arm (average approximately 661 patients per hospital). Based on national VA catheterization data for CKD patients,¹⁴ the proportion of AKI in the VLC and VLC+ASR arms are assumed to be 0.2700 under the null hypothesis and 0.2025 under the alternative hypothesis (an effect size of 25% or 0.0675). The proportion of AKI in TA and TA+ASR arms are projected at 0.2700 for the intervention period. We further assume an intra-cluster correlation coefficient (the ratio of variation between hospitals to the sum of variation within and between hospitals) of 0.0009 – this is implied by the intervention arm of the pilot study.³ We plan to conduct 0.05-level tests and desire

PROTOCOL

(Version #: 6, version date: 9-21-20)

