power of at least 90%. The power for analysis to detect any difference at all across the four intervention studies can be approximated by assuming the distribution of the proportion of AKI cases under each strategy follows a normal distribution and applying an F-test with penalty for clustering. Under these assumptions, our power to detect any difference against the null of no difference is above 99%. We also compute power for illustrative individual contrasts of interest. The power to detect a significant effect of VLC within a level of ASR (i.e., either for ASR used or ASR not used) is also above 99% (although numerically lower than for the test of any difference across the four groups as sample size is halved) with a minimum detectable effect size of 0.034. If under the alternative hypothesis the proportion of AKI for the VLC arm was also 0.27 (so that an interaction effect is present), the power to detect a significant interaction between TA/VLC and ASR status is just above 90%. Power is lower for the interaction contrast due to four groups being compared as opposed to only two groups. In summary, we have overwhelming power to detect a difference among any of the four intervention strategies and between the levels of one factor within a level of the other factor, and acceptable power (i.e., above 90%) to detect a significant interaction between the effects of the factors. Finally, assuming a Bonferroni correction for multiple testing and a 25% effect size for each difference, testing the full set of 6 pairwise differences among the four intervention strategies has power >97% implying we will be adequately powered to infer the optimal intervention strategy.

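### The Satterthwaite correction does not protect the type I error unless the SAP also names a REML-type estimator for the hospital variance

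*SAP*

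**What the plan says.** The unit of randomisation is the hospital: "Randomization will occur at the hospital level in a 2x2 factorial design" (Protocol C.2.b). The site criteria in C.2.a say that 29 sites were over-recruited, "but a minimum of 16 VA sites will be enrolled", and C.11 plans "with four hospitals within each arm (average approximately 661 patients per hospital").

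The SAP analyses patient-level data with a hierarchical logistic model in which "observations were clustered at the site level, and models included a site-level random effect". It also adjusts for each site's baseline observed-to-expected (O/E) ratio. On the small number of hospitals it says only: "We implemented Satterthwaite small-sample correction because of the small number of clusters". Pairwise odds ratios are Bonferroni-corrected. The interaction and the differences among the four combinations are named as the features of main interest.

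The SAP does not state the estimator of the hospital variance, the covariance matrix to which the Satterthwaite degrees of freedom (df) attach, or what is done when the variance is estimated as zero. Protocol C.7 gives the model equation but names no estimator and no small-sample correction.

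**The concern.** Two things go wrong when few hospitals are analysed with a random-effects model: the hospital variance is itself poorly estimated, and ML estimates it too low because it ignores the df spent on hospital-level coefficients. Satterthwaite deals with the first by using a t reference in place of the normal. It does nothing about the second, because the standard error in the test statistic is unchanged.

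The SAP model has five hospital-level coefficients (intercept, three arm terms, baseline O/E), so 16 hospitals leave 11 residual df. All six pairwise odds ratios and the interaction depend on this variance. If it is too small, intervals are too narrow. Bonferroni then divides an error rate that is already above nominal, and one implementation strategy could be declared better than another by chance.

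**Working it through.** **Inputs from the documents.** Four hospitals per arm, mean 661 patients, 2,644 per arm, ICC 0.0009, AKI 0.27 against 0.2025 (C.11). The level and power target are in C.11: "We plan to conduct 0.05-level tests and desire" "power of at least 90"%. Sidedness is not stated, so two-sided is used. Table 1 volumes run from 49 to 1,794. Bonferroni over six pairs gives 0.05/6 = 0.0083.

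**1. The plan's own power figures.** Design effect = 1 + 660 × 0.0009 = 1.594. Effective n per arm = 2,644/1.594 = 1,659.
- Pairwise SE = √[(0.27×0.73 + 0.2025×0.7975)/1,659] = 0.0147, and 0.0675/0.0147 = 4.59. Power at 5% = Φ(4.59 − 1.96) = 99.6% (stated: above 99%).
- At 0.0083: Φ(4.59 − 2.64) = 97.5% (stated: above 97%).
- Interaction (three arms at 0.27, one at 0.2025): SE = 0.0213, ratio 3.17, power Φ(3.17 − 1.96) = 88.7% (stated: just above 90%).

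The pairwise figures reproduce, and the interaction comes within two points. All use a normal reference.

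**2. Closed form for ML, when hospital variance dominates.** ML divides by 16 where an unbiased estimate divides by the residual df, so the SE is too small by √(rd/16). Actual error = P(|T_rd| > t_ref × √(rd/16)). The ML-based Satterthwaite df come out near 16.
- 11 residual df, reference df 16: 2.120 × 0.829 = 1.758, error 10.7%.
- 11 residual df, reference df 11: 2.201 × 0.829 = 1.825, error 9.5%.
- 12 residual df (no O/E term): 9.1% with reference df 16, 8.4% with reference df 12.

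Even the correct reference df therefore leave the ML test inflated.

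**3. Null simulation of the logistic model.** 16 hospitals, AKI 0.27, binomial counts, normal hospital effect on the logit scale, 4,000 trials per scenario (Monte Carlo SE about 0.2–0.3 points), baseline O/E in the model. Satterthwaite df = 2V²/Var(V). Ranges run from formula df throughout to a normal reference when the variance is estimated as zero. Figures are % rejected at nominal 5%: per pair / familywise after Bonferroni.

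| Sizes | ICC | ML (Laplace) | REML-type |
|---|---|---|---|
| equal | 0.0009 | 5.9–7.2 / 4.0–7.6 | 3.5–4.3 / 1.6–3.8 |
| equal | 0.003 | 9.4–9.9 / 9.3–11.0 | 4.6–4.8 / 2.9–3.6 |
| equal | 0.01 | 10.6 / 11.4–11.5 | 4.9 / 3.5–3.6 |
| equal | 0.02 | 11.0 / 12.2 | 5.3 / 4.0 |
| equal | 0.05 | 10.5 / 11.5 | 4.9 / 3.3 |
| unequal | 0.0009 | 7.6–9.4 / 6.1–11.4 | 3.6–5.1 / 1.2–4.5 |
| unequal | 0.003 | 11.3–12.2 / 11.6–15.2 | 4.8–5.4 / 2.8–4.6 |
| unequal | 0.01 | 11.4–11.5 / 12.7–13.0 | 4.9 / 3.4–3.5 |
| unequal | 0.02 | 10.6 / 11.1 | 4.8 / 3.0 |
| unequal | 0.05 | 10.1 / 10.4 | 4.5 / 3.1 |

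Without the O/E term and with equal sizes, ML gave 6.8–7.9% per pair at ICC 0.0009 and 8.5–9.2% at 0.003–0.05. Its mean hospital variance was 0.47 of the truth at ICC 0.0009 and 0.75 (= 12/16) at 0.05; the REML-type ratio was 1.00–1.03.

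The zero-variance rule matters. At ICC 0.0009, ML with the O/E term put the variance at zero in 55% of trials with equal sizes and 67% with unequal sizes. Reverting to a normal reference there moves familywise error from 6.1% to 11.4% in the unequal case.

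A separate simulation with five site-level coefficients agreed. ML with Satterthwaite gave 7.4–8.0% per pair and 5.5–6.6% familywise at ICC 0.0009, and 10.4–11.6% and 10.5–13.0% at 0.003–0.02. REML-type gave 3.6–5.3% and 1.4–4.4%.

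**4. Power on the residual hospital df.** With t on 11 df, the critical value at 0.0083 is 3.21 in place of 2.64. The noncentral t with noncentrality 4.59 then gives 88.5%. For the interaction at 5% (critical value 2.20, noncentrality 3.17) it gives 82%. Neither allows for covariate gain.

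**The case against.** A reader might infer that the SAP's pairwise tests do reject 8–12% of the time. The documents do not support that. The SAP names no estimator, and with a REML-type variance the very same sentence describes tests that hold their level. ML is inferred from common practice, not from the text.

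Three further points stand. The only ICC in the documents is 0.0009. There, with equal hospitals, ML gives 5.9–7.9% per pair, and familywise error, which is what the SAP controls, is close to nominal in most runs. Sixteen hospitals is a minimum, and more would shrink the bias. Nor is there any need to demote the prespecified patient-level model, since changing the variance estimator is enough.

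Against this, 0.0009 comes from one arm of a pilot in 10 hospitals. It implies that 95% of hospitals have AKI rates between about 24.5% and 29.7%; an ICC of 0.003 needs only about 22.5% to 32%. The protocol reports five-fold variation across hospitals (Objective) and, after risk adjustment, 8 VA sites worse than expected and 7 better for part of a five-year period (A.4). Case mix and chance contribute to the first figure, and O/E adjustment removes some variation. These facts do not fix an ICC, but they make values above 0.0009 plausible.

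**Conclusion.** The concern holds conditionally. The SAP recognises the few-cluster problem, but its stated remedy covers only half of it, and whether the tests are valid depends on a choice the SAP leaves open.

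Under ML/Laplace with 16 hospitals, per-pair error is about 6–9% at ICC 0.0009, with familywise error about 4–7% in most runs and up to 11.4% with unequal hospitals and a normal reference at zero variance. At ICCs of 0.003 or more it is about 8.5–12% per pair and roughly 9–15% familywise. Under a REML-type fit it is 3.5–5.4% per pair and 1.2–4.6% familywise in every scenario. An actual inflation in this trial is not shown.

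Assumptions not in the documents: ICCs above 0.0009; a correlation of 0.5 between baseline O/E and the hospital effect; CKD patient numbers proportional to Table 1 volumes in the unequal runs. The 20 patient covariates were not simulated, and only the CKD rate of 0.27 was used, so the whole-population analysis was not examined.

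**What to change.** Keep the patient-level logistic model as primary and add to the SAP:
- The hospital variance is estimated by a REML-type method (restricted or pseudo-likelihood), and the software implementation is named.
- Satterthwaite df are computed from that fit and capped at the residual hospital df: 16 − 5 = 11, more if more hospitals are enrolled, fewer if further site terms are added. The cap also applies when the variance is estimated as zero, with no return to a normal reference.
- As a sensitivity check, a hospital-level analysis of case-mix-adjusted log-odds on the arm terms and baseline O/E, weighted by precision because volumes differ widely, on the same df.
- Any permutation test re-randomises all hospitals within the region and volume blocks. Re-allocating only the two arms compared gives C(8,4) = 70 allocations, so the smallest two-sided p is 2/70 = 0.029, which cannot reach 0.0083. The full re-randomisation tests equality of all four arms, so it supports the overall comparison more directly than any single pair.

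The cost is a few sentences and one short extra analysis. Intervals widen. C.11 should be restated: at its own assumptions and before any covariate gain, Bonferroni pairwise power is about 89% on 11 df, not above 97%, and interaction power about 82%, not just above 90%.
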